7.2 Classification of an Adverse Event

7.2.1 Assessment of Severity

The descriptions and grading scales found in the revised NCI-CTCAE version 5.0 will be utilized for AE reporting. A copy of these criteria can be downloaded from the website: https://ctep.cancer.gov/protocoldevelopment/electronic_applications/ctc.htm.

- **Grade 1:** Mild; asymptomatic or mild symptoms; clinical or diagnostic observations only; intervention not indicated
- **Grade 2:** Moderate; minimal, local or noninvasive intervention indicated; limiting age appropriate instrumental ADL*

CONFIDENTIAL Compound: SL-172154

- **Grade 3:** Severe or medically significant but not immediately life-threatening; hospitalization or prolongation of hospitalization indicated; disabling; limiting self-care ADL**
- Grade 4: Life-threatening consequences; urgent intervention indicated
- Grade 5: Death related to AE

*Instrumental activities of daily living (ADL) refer to preparing meals, shopping for groceries or clothes, using the telephone, managing money, etc.

** Self-care ADL refer to bathing, dressing and undressing, feeding self, using the toilet, taking medications, and not bedridden.

For AEs not included in the NCI-CTCAE v5.0 grading system, the following guidelines will be used to describe severity.

- Mild Events require minimal or no treatment and do not interfere with the subject's daily activities.
- **Moderate** Events result in a low level of inconvenience or concern with the therapeutic measures. Moderate events may cause some interference with functioning.
- Severe Events interrupt a participant's usual daily activity and may require systemic drug therapy or other treatment. Severe events may be potentially life-threatening or incapacitating.

NOTE: A distinction should be drawn between serious and severe AEs. Severity is an estimate or measure of the intensity of an AE, while the criteria for serious AEs are indications of adverse subject outcomes for regulatory reporting purposes. A severe AE need not necessarily be considered serious and a serious AE need not be considered severe.

7.2.2 Assessment of Causality

The clinician's assessment of an AE's relationship to SL-172154 is part of the documentation process, but it is not a factor in determining what is or is not reported in the study. If there is any doubt as to whether a clinical observation is an AE, the event should be reported. All AEs must have their relationship to SL-172154 assessed. In a clinical trial, the IP must always be suspect. To help assess causality, the following guidelines are used.

- **Related** The AE is known to occur with the IP, there is a reasonable possibility that the IP caused the AE, or there is a temporal relationship between the IP and event. Reasonable possibility means that there is evidence to suggest a causal relationship between the IP and the AE.
- Not Related There is not a reasonable possibility that the administration of IP caused the event, there is no temporal relationship between IP and event onset, or an alternate etiology has been established.

7.2.3 Expectedness

The Sponsor will be responsible for determining whether an AE is expected or unexpected.

• Unexpected - An AE will be considered unexpected if the nature, severity, or frequency of the event is not consistent with the safety information section 6.0 (Guidance for Investigators) of the IB [Report_SL2020IB001] for the IP. "Unexpected," as used in this

definition, also refers to AEs or ARs that are mentioned in the IB as occurring with a class of drugs or as anticipated from the pharmacological properties of the drug not specifically mentioned as occurring with the IP under investigation.

• **Expected** - AEs that are common and known to occur for the IP being studied. Expectedness refers to the awareness of AEs previously observed, not on what might be anticipated from the properties of the IP.

7.3 Timing for Event Assessment and Follow-up

All AEs occurring while on study must be documented appropriately regardless of relationship. All AEs will be followed to adequate resolution. The occurrence of an AE or SAE may come to the attention of study personnel during study visits and interviews of a study subject presenting for medical care, or upon review by a study monitor.

Any medical condition that is present at the time that the subject is screened will be considered as baseline and not reported as an AE. However, if the pre-existing condition deteriorates at any time after the subject signs the main study ICF, it will be recorded as an AE. Unanticipated problems will be recorded in the data collection system throughout the study.

AEs characterized as intermittent require documentation of onset and duration of each episode.

Event	Reporting Procedures
Adverse Event	Subjects will be followed continuously for AEs during the study and for 90 days after the last dose of IP. After a subject is discontinued from IP due to progressive disease or for other reasons, any ongoing AE should be followed until resolution (or return to baseline) and documented in the eCRF, regardless of whether the event(s) is attributed to trial medication. If another anticancer agent is started within 90 days of the last dose of SL-172154, only SAEs and irAEs that occur before the new anticancer therapy should be recorded. The following information will be recorded: description, date of onset and end date, severity, assessment of relatedness to trial medication, and action taken. Follow-up information should be provided as necessary. AEs will be followed either until resolution, or the event is considered stable.
	It will be left to the Investigator's clinical judgment to decide whether an AE is of sufficient severity to require the subject's removal from treatment. A subject may also voluntarily withdraw from treatment due to what he or she perceives as an intolerable AE. If either of these occurs, the subject must undergo an end of trial assessment and be given appropriate care under medical supervision until symptoms cease, or the condition becomes stable.

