 - 1) If subject has positive ADA test on D1 of cycle 13 or ADA results are not known, then follow up predose samples for PK/ADA should be collected every 3 cycles on D1 of subsequent treatment cycles (i.e., cycles 16, 19, 21 and 24) until ADA resolves to baseline OR until the last PK/ADA sample is collected within 105-125 days after the last dose of SL-172154.
 - A PK/ADA sample is collected within 7 to 30 days after the subject discontinues SL-172154 therapy. 5

- 3) If subject has positive ADA tests during treatment or ADA results are not known a final PK/ADA sample is collected within 105-125 days after the last dose of SL-172154.
 - Cytokines will be collected in cycle 2 on days 15 and 16 as depicted in Table 4 and on day 1 of cycle 3 as depicted in Table 5. 4
- Correlative laboratory studies: Refer to supplementary Table 6 for details in Section 6.1.2 plus see the SLM for amount of blood needed and sample shipment details. 'n.
 - Complement, Immunophenotyping and Receptor Occupancy
- SL-172154 administration: Subjects with confirmed CR who have had a minimum of 48 weeks of treatment may elect to discontinue SL-172154 and continue with all relevant study assessments including disease assessments. SL-172154 should be administered on D1, D8, and D15 according to the prescribed dosing schedule without deviation in cycle 1 to align with the safety DLT assessment and sample (PK, ADA, etc.) collection schedules Beginning on cycle 2, day 1, a window of +/- 1 day is allowed for scheduled dosing days for drug administration. o.
- discontinued from SL-172154 or study therapy due to progressive disease or for other reasons, any ongoing AE should be followed until resolution (or return to baseline) and documented in the eCRF. If another anti-cancer agent is started within 90 days after the last dose of SL-172154, only SAEs and AEs that occur prior to the start of the new anticancer therapy should be recorded. In the event of a continuing SAE or a non-serious irAE, the subject will be AE Monitoring: Subjects will be followed continuously for AEs during the study and for 90 days after the last dose of SL-172154. After a subject is asked to return for follow-up until the SAE or AE has resolved or is deemed to be continuing indefinitely. AEs will be characterized per NCI-CTCAE criteria v5.0 and events recorded in the eCRF. പ്

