7. SAFETY ASSESSMENTS

Subjects will be followed continuously for all AEs starting when a subject has signed the ICF, throughout the course of treatment and for 90 days after the last dose of IP. After a subject is discontinued from SL-172154 due to progressive disease or for other reasons, any ongoing AEs should be followed until resolution (or return to baseline) and documented in the eCRF. If another anti-cancer agent is started within 90 days after the last dose of SL-172154, only SAEs and AEs that occur prior to starting the new anticancer therapy should be recorded. All observed or volunteered AEs (serious or non-serious) and abnormal laboratory test findings, if applicable, whether suspected to have a causal relationship to SL-172154 or not will be recorded in the subject medical record and in the eCRF. AEs will be graded according to NCI-CTCAE v5.0. For all AEs, sufficient information will be pursued and/or obtained to permit an adequate determination of seriousness and outcome of the event (i.e., whether it should be classified as a SAE or not) and an assessment of the causal relationship between the AE and SL-172154. AEs will be followed until resolution (or return to baseline) or stabilization. Refer to Section 7.4 for documentation and reporting of AEs.

Event	Definition
Adverse Event (AE)	The AE observation period starts at the time of signing informed consent and includes
	baseline or washout periods, even if no study treatment has been administered.
	An AE is defined as any untoward medical occurrence in a subject to whom the IP has
	been administered, regardless of whether the event is considered related to that product.

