7.1 Definitions for Safety Parameters

Event	Definition
	An AE is also defined as an undesirable medical condition due to a study-related
	procedure.
Adverse Reaction (AR)	AR is an untoward and unintended response in a subject to an IP. A causal relationship
	between a trial medication and an AE is at least a reasonable possibility, i.e. the
C	relationship cannot be ruled out.
Serious Adverse	An AE or suspected AR that is considered "serious" if, in the view of either the
Event (SAE) or Serious Adverse Reaction	 investigator or Sponsor, it results in any of the following outcomes: Death (Note: death is an outcome not an event)
(SAR)	 A life-threatening AE (an event in which the subject was at risk of death at the time
	of the event; it does not refer to an event which hypothetically might have caused
	death if it were more severe)
	 Inpatient hospitalization or prolongation of existing hospitalization
	• A persistent or significant incapacity or substantial disruption of the ability to
	conduct normal life functions
	• A congenital anomaly/birth defect.
	• Important medical events that may not result in death, be life-threatening, or require
	hospitalization may be considered serious when, based upon appropriate medical
	judgment, they may jeopardize the participant and may require medical or surgical
	intervention to prevent one of the outcomes listed in this definition. Examples of such
	medical events include allergic bronchospasm requiring intensive treatment in an
	emergency room or at home, blood dyscrasias or convulsions that do not result in inpatient hospitalization, or the development of drug dependency or drug abuse.
Laboratory test(s) that	 Any laboratory test result that meets the definition of an AE or SAE or requires
meet definition of an	holding or discontinuation of IP or requires corrective therapy, must be documented
AE or SAE:	appropriately.
	• Ad hoc labs should be collected as noted in Section 6.4.6.1 above if IRR/CRS
	occurs.
	The investigator must review the laboratory report, document this review, and record
	any clinically relevant changes occurring during the study in the subject's medical
	record and recorded in the AE section of the eCRF. The laboratory reports must be filed
	with the source documents. Clinically significant abnormal laboratory findings are those which are not associated with the underlying disease unless judged by the investigator

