7.1.1 Events not Qualifying as AEs/SAEs

Because attribution of AEs is difficult in a FIH study, any toxicity experienced by subjects in this study should be recorded as AEs unless otherwise specified. The following are not considered to be AEs or SAEs:

- Medical or surgical procedures (e.g., endoscopy, appendectomy). The condition that leads to the procedure is considered the AE.
- Elective procedures, planned hospitalizations, and procedures for treatment of conditions noted in the subject's medical history (present prior to signing the ICF) that have not worsened are not considered AEs.
- Situations where an untoward medical occurrence did not occur (i.e., admission to hospital for social circumstances).
- Anticipated day-to-day fluctuations of pre-existing medical conditions that were present at start of study. These conditions are considered part of the subject's medical history and must be adequately documented on the appropriate page of the CRF.
- Clear progression of disease under study should not be reported as an AE or SAE (unless the investigator considers the progression of underlying neoplasia to be atypical in its nature, presentation or severity from the normal course of the disease in a particular subject). Signs and symptoms that are clearly consistent with the expected progression of the underlying cancer should not be reported as an adverse event, and hospitalizations due to the progression of cancer do not necessarily qualify for an SAE. If there is any uncertainty about an AE being due only to the disease under study, it should be reported as an AE or SAE.
- In the case where the medical condition is known when the participant enters the trial, only worsening (increased frequency or intensity of the episodes or attacks) will be documented as an AE. If the disease is detected during the trial, and if repeated episodes enable diagnosis of a chronic disease, the episodes will be grouped together in the CRF, and the diagnosis will be clearly described.
- Laboratory abnormalities: An isolated, out-of-range laboratory result in the absence of any associated, clinical finding may or may not be considered an AE, the Investigator's evaluation should be based on a consideration of the overall clinical context.

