8.2 Adverse Events

The AE terms on the eCRFs will be mapped to the preferred terms (PT) and system organ classes (SOC) using the Medical Dictionary for Regulatory Activities (MedDRA). Drug-related AEs are defined as AEs with relationship to study treatment being related or possible related. A worst-case scenario approach will be taken to handle missing data, i.e. AEs with the relationship to study treatment as missing will be treated as drug-related AEs.

All AEs with onset dates on or after the first dose of study treatment are defined as treatmentemergent adverse events (TEAEs). Only TEAEs will be included in AE tables.

An overview summary of TEAEs will be produced to include counts and percentages of subjects with any TEAE, drug-related TEAEs, DLT, serious TEAEs, drug-related serious TEAEs, fatal TEAEs, immune related TEAEs, infusion related reaction AEs, Grade 3 or 4 TEAEs, and TEAEs leading to drug withdrawn, drug interrupted, dose not given/held, and infusion interrupted.

The TEAE by maximum toxicity grade summary tables will use the following algorithms for counting subjects:

- **PT rows:** each subject is counted once within each unique PT at the maximum grade. For example, if a subject has two headaches, the subject is counted only once under the PT "Headache". Subjects experiencing the same TEAE PT several times with different grades will only be counted once with the maximum grade.
- **Any event row**: each subject with at least one TEAE will be counted only once at the maximum grade no matter how many events they have.

All TEAEs and drug-related TEAEs will be summarized by MedDRA PT and maximum toxicity grade. The PT will be ordered by descending order of the subject incidence based on all subjects in the analysis population. A table of all TEAEs by SOC and PT will also be provided.

The following summary tables will be presented by MedDRA PT, in which the PT will be sorted by descending order of subject incidence of PT based on all subjects in the analysis population:

- Summary of all TEAEs.
- Summary of drug-related TEAEs.
- Summary of Grade 3 or 4 TEAEs.
- Summary of DLT.
- Summary of TEAEs leading to drug interrupted, dose not given/held, infusion interrupted, and drug withdrawn.
- Summary of serious TEAEs.
- Summary of drug-related serious TEAEs.
- Summary of immune related TEAEs.

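### Protocol 7.4 records fewer adverse events than Protocol 7 and the schedule footnotes for subjects who start another anticancer agent within 90 days of the last dose

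*Protocol*

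**What the plan says.** Four places in the current protocol state what to record when another anticancer agent is started within 90 days of the last dose.

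- **Protocol 7.4**, adverse event row of the reporting table (its opening rows stand just above the 7.4 heading in the text version): "only SAEs and irAEs that occur before the new anticancer therapy should be recorded".
- **Protocol 7**: "only SAEs and AEs that occur prior to starting the new anticancer therapy should be recorded".
- **Protocol 6.1**, Schedule 1, footnote p: "only SAEs and AEs that occur prior to the start of the new anticancer therapy should be recorded".
- **Protocol 6.2**, Schedule 2, AE monitoring footnote: the same words as footnote p.

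Protocol 7 ends by referring the reader to 7.4 for how AEs are documented and reported. Protocol 7.3 adds a general rule: "All AEs occurring while on study must be documented appropriately regardless of relationship".

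Protocol 2 and SAP 2 both name the incidence of all AEs, and of irAEs, among the primary safety outcomes. SAP 8.2 works from the AE terms on the eCRF. Its definition of a treatment-emergent event begins "All AEs with onset dates on or after the first dose of study treatment are defined as", states no end to the window, and only such events enter the AE tables.

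**The concern.** The two rules cannot both be followed for one type of event: a non-serious AE, not labelled immune related, that starts after the last dose and before the new agent. Protocol 7 and the footnotes require it; 7.4 excludes it. The narrower rule sits in the section to which sites are sent for reporting.

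The primary safety outcome counts all AEs. If sites follow different sections, the treatment-emergent and drug-related tables for a dose level would combine subjects recorded under different rules. The omission would also be selective, because it falls only on subjects who move quickly to other treatment. The analysis cannot repair this, since an event that was never entered is not in the data.

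**Working it through.** The plan gives no figure to reproduce, so the check compares the texts and then scales the effect of one subject.

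**Which events differ.** For a subject who starts a new agent within 90 days of the last dose:

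| Event | Protocol 7 and schedule footnotes | Protocol 7.4 |
|---|---|---|
| SAE before the new agent | recorded | recorded |
| Non-serious irAE before the new agent | recorded | recorded |
| Other non-serious AE, last dose to new agent | recorded | not recorded |
| Any event starting after the new agent | not recorded | not recorded |

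Only the third row differs. The exposed interval runs from the last dose to the start of the new agent. It is therefore shorter than 90 days, and shortest for those who switch soonest.

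**An illustration.** Take a non-serious event, not immune related, on day 20 after the last dose. If no new agent is started, every section records it. If a new agent starts on day 60, Protocol 7 still records it and 7.4 does not. Under 7.4 the status of a day 20 event thus depends on a later treatment decision.

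**Size per subject.** SAP 8.2 counts a subject once per preferred term, so one omitted subject changes a term's incidence by at most 1/n:

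- n = 6, the lower end of the 6 to 12 subjects intended at the RP2D (Protocol 3.1.1): 1/6 = 16.7 points.
- n = 12, the upper end: 1/12 = 8.3 points.
- All subjects, planned 33 to 54: 1/33 = 3.0 points and 1/54 = 1.9 points.

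The change is zero if the subject already had that term on treatment.

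**How many subjects.** The documents give neither the proportion who start another agent within 90 days nor the rate of such events in the gap. A total cannot be calculated without assuming both.

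**What does not move.** DLTs are assessed in the first 28 days, when events would normally be recorded as they occur. A subject who stops and switches within those 28 days is a possible but rare exception. SAEs and irAEs are kept under both rules.

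**The case against.** The strongest reply is that little would be lost in practice. The same 7.4 cell first requires continuous AE follow-up through 90 days after the last dose. When an event starts, the site often does not know that a new agent is coming, so following 7.4 would often mean removing an entry already made. The Schedule 1 table marks AE collection at the post-treatment visit, which is held within 30 days of the last dose or before a new therapy. Three of the four statements of the rule require all AEs. This stands, and it is why the effect is probably small. It does not remove the conflict, because 7.4 read literally still excludes events that the other three places require.

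A reader might infer more than the documents support:

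- **That many subjects are affected.** Any count would rest on assumed switching and event rates, and would ignore events already entered or collected at the post-treatment visit.
- **That other sections settle the matter.** Protocol 7.2.2 says of the causality assessment that "it is not a factor in determining what is or is not reported in the study", but that concerns relationship to the drug, not immune-related status. Protocol 7.1.1 says "any toxicity experienced by subjects in this study should be recorded as AEs unless otherwise specified", and its closing words leave room for a specific rule such as 7.4.
- **That the irAE label is a second fault.** Protocol 7.1 has no irAE entry, and SAP 8.2 states no source for the label. This is missing detail. Protocol 3.6 presumes events without a clear alternative cause to be potentially immune related; read broadly, that would narrow the gap.
- **That the SAP is at fault.** This is a data-collection inconsistency in the protocol, and no SAP rule could recover events that were not entered.

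**Conclusion.** The conflict is real and stands in current text. The Amendment 02 summary of changes shows Protocol 7 itself with the irAE wording that it no longer carries. That would fit 7.4 having been left unaligned, but the point does not depend on it.

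The consequence is limited. Tables of all and drug-related treatment-emergent events could mix two capture rules for the period between the last dose and a new agent. One affected subject moves a preferred term by at most 17 points at n = 6 or 8 points at n = 12, provided the term is new for that subject. The number affected is unknown and probably small. A reader might infer that dose escalation or the MTD is biased; the 28-day DLT window makes that unlikely. The correction is worth making because it is specific and cheap and concerns a named primary outcome.

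**What to change.** In the adverse event row of the Protocol 7.4 table, change irAEs to AEs in the sentence quoted above, so that it agrees with Protocol 7 and both schedule footnotes. Make the change by clarification memo, a route that SAP 3.1 (footnote e of its Table 1) shows this study has already used, or with the next amendment. Then query sites, for subjects who started another agent within 90 days of the last dose, about any non-serious AE before that agent that was not entered.

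The cost is one word and one targeted query, with no new visits or samples. If the change goes through an amendment, Protocol 13.2 requires IRB/IEC approval before it is implemented, so it should travel with other changes. No SAP text or table needs to change for this point.
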